6.1.8.3 Management of Myelosuppression (Cytopenias)

Venetoclax

Myelosuppression and the related adverse events (thrombocytopenia, anemia, neutropenia, and febrile neutropenia) are common in both treated and untreated subjects with AML. Subjects with baseline neutropenia or have significant bone marrow involvement may be particularly at high risk. If a participant achieves a CR or CRi or is found to have a morphologically leukemia free bone marrow, and has Grade 4 neutropenia or thrombocytopenia, venetoclax should be held from Day 28 until ANC $\geq 500 - 1000/\mu\text{L}$ and platelets $\geq 25 - 100 \times 10^5/\mu\text{L}$. At the investigator's discretion, subjects may resume a subsequent cycle of therapy after a 2-week interruption if the investigator believes the risk of AML progression outweighs the risk of further treatment before cytopenia recovery. Typically, if morphologic AML remains in the bone marrow, concurrent cytopenias are thought to be attributable to the disease processes of AML. In subsequent cycles, if a subject in CR presents with new onset Grade 4 neutropenia or thrombocytopenia for more than 1 week, unless it is due to the underlying disease, venetoclax dosing may be interrupted until ANC recovery to $\geq 500 - 1000/\mu\text{L}$ or platelets $\geq 25 - 100 \times 10^5/\mu\text{L}$ per investigator discretion in consultation with the AbbVie medical monitor. Venetoclax may be re-initiated at a lower dose per discussion with the AbbVie medical monitor.

Administration of venetoclax in subjects with lymphoproliferative disorders has been associated with clinically significant lymphopenia (B and T lymphocyte subtypes). If clinically indicated in AML subjects treated in this study, anti-infective prophylaxis should be implemented at the investigator's discretion, including appropriate prophylaxis for viral, fungal, bacterial or Pneumocystis infections. Potential for drug-drug interactions should be considered. Please refer to [Table 1](#) and [Appendix C](#) for a description of excluded and cautionary medications.

If a subject is continuing to respond based on the bone marrow assessment beyond Cycle 2 of treatment but has persistent neutropenia or thrombocytopenia venetoclax dose may be reduced as follows:

Table 12. Dose Reduction Guidelines for Management of Persistent Neutropenia or Thrombocytopenia

Venetoclax Dose/Duration	Reduced Venetoclax Dose/Duration
600 mg daily × 28 day cycles	600 mg daily × 21 days with 7 day interruption
600 mg daily × 21/28 day cycles	600 mg daily × 14 days with 14 day interruption
600 mg daily × 14/28 day cycles	400 mg daily × 14 days with 14 day interruption

Standard Therapy: Low – Dose Cytarabine

In a recent international clinical trial, subjects receiving LDC experienced the following treatment emergent CTCAE grade 3 or 4 adverse events at a rate of at least 10%: thrombocytopenia 35%, anemia 27%, febrile neutropenia 25%, disease progression 22%, neutropenia 20%, pneumonia 19%, general physical health deterioration 16%, leukopenia 10%.³⁵ It is unknown whether the aforementioned adverse events are attributable to receiving treatment with LDC or were attributable to the underlying health condition of AML. Complications of myelosuppression, including infections and bleeding, may be exacerbated by treatment with LDC. During Cycle 2 and subsequent cycles, LDC treatment may be delayed at the discretion of the investigator, if the subject experiences myelosuppression associated complications, such as those described below:

- Febrile neutropenia (temperature $\geq 38.5^{\circ}\text{C}$ and ANC $< 1,000/\mu\text{L}$)

- Active viral, bacterial or fungal infection (i.e., requiring IV anti-infectives or extensive supportive care)
- Hemorrhage (gastrointestinal, genito-urinary, pulmonary with platelets < 25,000/ μ L or any central nervous system hemorrhage)

Treatment with LDC may be resumed once the above conditions have improved or have been stabilized with adequate treatment (anti-infective therapy, transfusions, or growth factors).

Myelosuppression caused by LDC is reversible. Complete blood and platelet counts should be performed regularly, as clinically indicated and prior to each treatment cycle. In the presence of myelosuppression or its complications, treatment with LDC may be interrupted or supportive measures instituted.

LDC dose reductions are not typically recommended. If a dose reduction is believed to be necessary a discussion with the AbbVie medical monitor is required.

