For this trial, DLTs are defined as experiencing a CTCAE grade 4 toxicity, unless such events are in the common list of health events due to AML ([Appendix F](#)), or not recovering platelets to at least $25,000/\mu\text{L}$ and ANC to $500/\mu\text{L}$ within 14 days of the last dose of venetoclax unless such cytopenias are due to residual leukemia effect. Should 1 subject experience a DLT, an additional 3 subjects will be enrolled at the same dose level (a total of 6 subjects at this dose level). Should 2 subjects at a dose level experience a DLT, that dose level is considered too toxic. The dose level below the too toxic dose level is considered the MTD. Additional subjects are then enrolled at the MTD to bring the total number enrolled at the MTD to 6. If during this cohort expansion, a total of 2 subjects at this dose level also experience a DLT, this level would also be considered too toxic and the method continues thusly until the maximal dose level is achieved where 6 subjects can be treated through Cycle 1 and no more than one subject experiences a DLT. Additional subjects may be enrolled at the current dose level at the discretion of the AbbVie medical monitor, if enrolled subjects are not evaluable. In addition, significant

adverse events occurring after Cycle 1 in previous dose levels and ongoing PK assessments may inform dose escalation decisions and should such unanticipated occurrences necessitate a modification to the planned cohort dose assignments, decisions will be communicated in writing to all investigators.

Dose Escalation Guidelines

Number of Subjects with DLT	Dose Escalation
0 of 3	Begin enrollment in the next dose level
1 of 3	Enroll 6 subjects in current dose level
1 of 6 or < 33% DLTs	Begin enrollment in the next dose level
≥ 2 of 6 or ≥ 33% DLTs	Previous dose determined as the MTD or dose de-escalation

If a dose de-escalation occurs and < 33% of subjects enrolled experience a DLT at the reduced designated cohort dose, this dosing regimen will be declared the MTD. If ≥ 33% of the subjects enrolled at the reduced designated cohort dose still experience a DLT, dose de-escalation of the designated cohort dose regimen will continue to be explored.

The MTD will be defined as the highest designated cohort dose level (and corresponding ramp-up period regimen, if applicable) at which < 33% of the subjects enrolled experience a DLT.

[figure not shown]

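### Protocol 6.1.8.3 prints the platelet level for resuming held venetoclax as 25–100 × 10⁵/µL (2.5 to 10 million) in both hold rules, so the first rule's recovery criterion cannot be met as printed; probably a typographical error

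*Protocol*

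**What the plan says.** Section 6.1.8.3 has two hold rules for venetoclax, and both carry the same platelet figure.

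- **First rule** (CR, CRi or leukemia-free marrow, with Grade 4 neutropenia or thrombocytopenia): "venetoclax should be held from Day 28 until ANC $\geq 500 - 1000/\mu\text{L}$ and platelets $\geq 25 - 100 \times 10^5/\mu\text{L". Neutrophils and platelets are joined by "and".
- **Second rule** (later cycles, new Grade 4 neutropenia or thrombocytopenia lasting more than a week in a subject in CR): dosing may be interrupted until the ANC recovers "or platelets $\geq 25 - 100 \times 10^5/\mu\text{L}$ per investigator discretion in consultation with the AbbVie medical monitor".

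Three other provisions in the section bear on resumption:

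- After a 2-week interruption the investigator may start another cycle if the risk of AML progression is judged greater than "the risk of further treatment before cytopenia recovery".
- Under the second rule, "Venetoclax may be re-initiated at a lower dose per discussion with the AbbVie medical monitor".
- For a subject still responding beyond Cycle 2 who "has persistent neutropenia or thrombocytopenia venetoclax dose may be reduced as follows", Table 12 gives reduced schedules, the first being "600 mg daily × 21 days with 7 day interruption".

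Elsewhere the platelet scale is different. The dose-limiting toxicity rule in Section 5.1 refers to "not recovering platelets to at least $25,000/\mu\text{L}$ and ANC to $500/\mu\text{L}$ within 14 days" of the last venetoclax dose. The cytarabine delay rule, also in 6.1.8.3, uses "pulmonary with platelets < 25,000". Section 5.3.3 sets platelets at 0.25 × 10⁵/µL for hematologic response, 0.5 × 10⁵/µL for CRh and 10⁵/µL for CR.

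**The concern.** This threshold tells a site when a subject in remission has recovered enough to restart drug. At 2.5 million platelets per microlitre or more, a responder with fully recovered counts still fails the first rule. On a literal reading the hold continues although the reason for it has gone.

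Section 5.4.1 gives this some weight. Among the reasons for which an investigator discontinues a subject, it lists a toxicity related to study drug that needs a venetoclax interruption of more than 4 weeks. A recovery criterion that cannot be reached sits badly beside that limit.

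**Working it through.** The plan makes no calculation here. The check is a unit conversion followed by a comparison with the protocol's other platelet levels.

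**Printed range**

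- Lower bound: 25 × 10⁵ = 2,500,000/µL
- Upper bound: 100 × 10⁵ = 10,000,000/µL

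**Other platelet levels against the printed lower bound**

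| Use | Protocol section | Platelets (/µL) | ANC paired with it (/µL) | Share of 2,500,000 | Lower bound ÷ level |
|---|---|---|---|---|---|
| Dose-limiting toxicity recovery | 5.1 | 25,000 | 500 | 1% | 100 |
| Hematologic response | 5.3.3 | 25,000 | 500 | 1% | 100 |
| Hemorrhage, cytarabine delay | 6.1.8.3 | below 25,000 | none | 1% | 100 |
| CRh | 5.3.3, 8.1.3.1.1 | 50,000 | 500 | 2% | 50 |
| CR | 5.3.3 | 100,000 | 1,000 | 4% | 25 |

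**Can the printed level be reached?** The documents give no normal platelet range, so one has to be assumed. With an upper limit of normal of 400,000 to 500,000/µL, the printed lower bound is 2,500,000/400,000 = 6.25 to 2,500,000/500,000 = 5.0 times that limit. Against an assumed 1,000,000/µL it is still 2.5 times higher.

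**What value fits?** With 10³ the range becomes 25 × 10³ = 25,000 to 100 × 10³ = 100,000/µL. The neutrophil range in the same sentence, 500–1000/µL, points the same way. Hematologic response pairs ANC 500 with platelets 25,000, and CR pairs ANC 1,000 with platelets 100,000. Those pairs are the two ends of the printed ranges once platelets are read in thousands. A lost decimal (0.25–1.0 × 10⁵) gives the same 25,000–100,000/µL.

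**Effect on each rule.** The first rule needs both counts, so the platelet figure alone defeats it. The second needs either count, so it can be met on neutrophils. Its platelet value is just as unusable, which matters most for a subject held for isolated thrombocytopenia.

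**Do the other provisions supply the missing criterion?** The 2-week route is for restarting before recovery. Table 12 is for cytopenia that persists, and it reduces the schedule or dose. Re-initiation under the second rule is at a lower dose. None says when a recovered responder under the first rule may resume.

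**The case against.** The strongest objection is that everything turns on one superscript in text read from a PDF by a program. Superscripts nearby are not fully reliable. In the same section, the adverse event rates from a recent international low-dose cytarabine trial carry citation 35, which the reference list gives as a 1987 review; Section 3.1 cites the international trial as 30. That may be a misread digit or a sponsor citation error, and the text cannot show which. Two near-identical strings in one paragraph could also be misread in the same way. The evidence that 25,000–100,000/µL is intended fits a misread as well as a typing error.

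This stands as a condition on the point. A misread is possible but not shown: the exponent is the same in both sentences, and 10³ and 10⁵ read sensibly side by side in the CR definition in Section 5.3.3. The plain-digit cut-offs in 5.1 and 6.1.8.3, which no superscript fault can touch, confirm the intended scale whichever explanation is right.

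A second objection is that the threshold is soft. Both counts are given as ranges, the first rule says "should", the second is discretionary, and a site would probably recognise the figure as impossible. That is fair and keeps the point small. It does not make the printed figure usable.

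A reader might also infer more than the documents support:

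- *That responders cannot be re-dosed, or must be discontinued.* The 2-week route, Table 12 and lower-dose re-initiation all allow treatment, and Section 5.4.1 leaves discontinuation to the investigator's judgement.
- *That sites would have to record resumption under a provision for unrecovered subjects.* Nothing in the documents requires a site to record which provision it relied on.
- *That reach can be judged by setting completed enrollment in the efficacy SAP (Section 5.0, Table 1) against the October 2020 protocol date.* Section 6.1.8.3 is not among the changes listed in Appendix I, so the wording predates this amendment. The comparison does not show how many subjects came under it.

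**Conclusion.** The point holds as a suspected typographical error in an operative dosing threshold; it is not a faulty calculation. As printed, the platelet level is 25 to 100 times the CR level, and the first hold rule's recovery criterion cannot be met. The second rule remains satisfiable through neutrophils. Read literally, the first rule prolongs holds in recovered responders and brings them closer to the 4-week interruption limit, although the investigator can end a hold sooner.

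Severity is minor. The error leans toward withholding drug, the likely value can be worked out from other sections, and no endpoint, sample size or analysis depends on it.

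The conclusion rests on two assumptions: that the source PDF prints 10⁵, and that platelet counts of 2.5 million/µL are out of reach in these subjects. If the PDF prints 10³, there is no error and the point falls. That 25,000–100,000/µL is the intended range is an inference from the rest of the protocol, so the sponsor should confirm it.

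**What to change.** Check the exponent in the source PDF. If it is 10⁵, change both sentences in Section 6.1.8.3 to platelets ≥ 25–100 × 10³/µL, preferably with 25,000–100,000/µL written out so that the unit cannot be mistaken. The sponsor should confirm the clinical value, and sites should receive a short clarification.

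The cost is one exponent in two sentences plus the site notice, which can go with the next amendment or administrative change. No analysis needs to be revised.

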Subjects should experience a DLT and/or complete at least 80% of indicated venetoclax and cytarabine dosing in the first cycle to be considered evaluable regarding dose modification decisions.

Transition from Phase 1 to Phase 2

Once the MTD is determined, enrollment into the dose escalation portion of the study will end. The dose level for the Phase 2 cohort will be communicated to all participating investigators prior to the start of Phase 2 enrollment. Subjects from the dose escalation portion of the study are not eligible for enrollment in the Phase 2 portion of the study.

Dosing Schema for Initial Phase 2

[figure not shown]
Figure 9. Dose Level 1 Cycle 1 (Starting Dose Level)

* Cycle = 28 days. Venetoclax dose will be administered on Day 1 – Day 28 starting with Cycle 2, at the designated cohort dose of 600 mg.

Dosing Schema for Phase 2 Cohort C

Figure 10. Phase 2 Cohort C**

* Cycle = 28 days. Venetoclax dose will be administered at the designated cohort dose of 600 mg on Day 4 – Day 28 of Cycle 1 and on Day 1 – Day 28 for all cycles starting Cycle 2.

** Applies to subjects enrolled in Amendment 2.

Dosing Schedule Overview – Venetoclax – Initial Phase 2 Portion and Phase 2 Cohort C

Once the MTD is declared, and the RPTD determined, a cohort of up to approximately 50 – 100 additional eligible subjects will be enrolled at the RPTD in order to further define the toxicity profile and to estimate the efficacy of the combination.

Subjects enrolled in the initial Phase 2 portion will receive the RPTD of venetoclax that will be administered orally once daily (QD) on Days 2 through 28 of Cycle 1 of the 28-day cycle. Beginning with Cycle 2, venetoclax will be administered Days 1 through 28 of each 28-day cycle. Cytarabine 20 mg/m²/QD will be administered on Days 1 – 10 of each cycle.

Subjects enrolled in Phase 2 Cohort C will receive venetoclax on Days 1 through 28 of each 28-day cycle, including Cycle 1. Cytarabine 20 mg/m²/QD will be administered on Days 1 – 10 of each cycle.

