Each dose of venetoclax should be taken with approximately 240 mL of water within 30 minutes after the completion of a meal, preferably breakfast. The dose should be administered at approximately the same time each day. On days the subject is given LDC, venetoclax should be given prior to LDC. The regimen is designed to escalate the dose of venetoclax in combination with LDC rapidly toward the target dose to optimize the opportunity for achieving a response and enable close subject monitoring. The dosing regimen will also enable interruptions, reductions (if necessary) and a slower intra-subject dose escalation if rapid tumor lysis or other toxicities are observed.

The initial period, approximately one week, of therapy until the target dose of venetoclax is achieved is considered the venetoclax ramp-up period (e.g., Day 1 through Day 4 of Cycle 1 in Phase 2 Cohort C).

Dose modifications of venetoclax in the ramp-up period may be implemented for individual subject(s) at risk for TLS or any new adverse events > Grade 2. Dose reductions must follow original dosing schema. If the subject requires dose reductions or dose holds during the venetoclax ramp-up period, a discussion with the AbbVie medical monitor is required.

To mitigate the potential risk of TLS,³⁶ subjects will receive TLS prophylaxis prior to any venetoclax dose escalation in combination with LDC. Subjects will be hospitalized during the ramp-up period, Day –1 through 24 hours post highest cohort dose (e.g., Day –1 through Day 5 of Cycle 1 in Cohort C). Tumor lysis syndrome prophylaxis will be initiated in all subjects starting at least the day prior to the first dose of venetoclax. Refer to Section 6.1.8.2, Management of Tumor Lysis Syndrome, for the details on TLS prophylaxis, [Appendix E](#) – Recommendations for Initial Management of Electrolyte Imbalances and Prevention of Tumor Lysis Syndrome (TLS) for procedures to follow, and [Appendix H](#) for information regarding how to recognize laboratory and clinical TLS.

If a subject develops any laboratory changes suggestive of TLS within the first 24 hours after either the first dose or during dose escalation, venetoclax dose escalation should be withheld or the dose should be reduced. Dose reductions and dose holds during the ramp-up period require notification of the AbbVie medical monitor as do any occurrence of clinical TLS.

Option to Continue Venetoclax Treatment

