5.2.3 Prior and Concomitant Therapy

If a subject reports taking any over-the-counter or prescription medications, vitamins and/or herbal supplements or if administration of any medication becomes necessary, from the Screening Visit through the end of the study, the name of the medication, dosage information including dose, route and frequency, date(s) of administration including start and end dates, and reason for use must be recorded on the appropriate electronic case report form (eCRF).

The AbbVie medical monitor identified in Section 6.1.6 should be contacted if there are any questions regarding concomitant or prior therapy(ies).

General guidelines regarding excluded and cautionary medications are summarized in [Table 1](#).

Table 1. Excluded and Cautionary Medications and Dietary Restrictions (See Appendix C for Examples of the Medications)

Excluded Foods During Ramp-Up and Throughout Study

 • Grapefruit and grapefruit products • Seville Oranges (including marmalade containing Seville oranges) • Starfruit
Excluded Medications During Venetoclax Ramp-Up Phase and Throughout Study:

 • Strong CYP3A inducers
Cautionary

 • Moderate or Strong CYP3A inhibitors 
 - Consider therapeutic alternative medications whenever appropriate. -If a subject requires use of these medications, limit the duration to the minimal duration medically required and reduce the venetoclax dose by at least 2-fold for moderate inhibitors and by at least 8-fold for strong inhibitors (see Table 2). After discontinuation of a moderate or strong CYP3A inhibitor, wait for 2 to 3 days before venetoclax dose is increased back to the initial target dose. • Moderate CYP3A inducers 
 -Exclude during the ramp-up phase and consider alternative medications. -If a subject requires use of these medications at the cohort designated dose, use with caution and contact the AbbVie medical monitor for guidance.

 • Warfarin* • P-gp substrates • BCRP substrates • OATP1B1/1B3 substrates • P-gp inhibitors • BCRP inhibitors

* Closely monitor the international normalized ratio (INR).

Table 2. Dose Modifications for Venetoclax: Moderate and Strong CYP3A Inhibitor Use

Assigned Venetoclax Dose	Dose if Co-Administered with a Moderate CYP3A Inhibitor	Dose if Co-Administered with a Strong CYP3A Inhibitor

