6.1.8 Toxicity Management

6.1.8.1 Definition – Dose Limiting Toxicity

Dose limiting toxicities (DLTs) for dose-escalation purposes will be determined during Cycle 1 (4 weeks) of study treatment. Adverse events that occur after the first cycle will also be evaluated by the investigator and the AbbVie medical monitor and may be considered as dose limiting.

Any of the following events, which cannot be attributed by the investigator to a clearly identifiable cause such as tumor progression, underlying illness, concurrent illness, or concomitant medication, will be considered a DLT:

- Grade 4 or 5 non-hematologic toxicity considered at least possibly related to the study drug, except those listed in [Appendix F](#).
- Grade 4 or 5 pancytopenia with a hypocellular bone marrow and no greater than or equal to 5% marrow blasts lasting for 42 days or more.

Any DLT will require an interruption and possible discontinuation of venetoclax or LDC. Venetoclax and LDC therapy may be reintroduced at a reduced dose, if the toxicity grade returns to \leq Grade 1 or to baseline if Grade 2 at study entry.

Any reduced dose level will be jointly defined by the investigator and the AbbVie medical monitor. The dose may be increased thereafter upon joint determination of the investigator and the AbbVie medical monitor. This dose is not to exceed the highest tolerated dose level. All decisions regarding continued dosing for individual subjects will

be medically managed by the investigator, per discussion with the AbbVie medical monitor, as appropriate. These decisions will be driven by the definition of DLTs as described above.

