6.1.8.5 Management of Other Toxicities

If other events occur that are related to venetoclax or LDC the investigator, in consultation with the AbbVie medical monitor, may interrupt or dose reduce venetoclax and/or reference therapy, as appropriate. Grade 3 or greater nonhematologic toxicity (e.g., nausea, vomiting, and diarrhea when additional supportive care fails), that is related to venetoclax or LDC will require interruption and possible discontinuation of dosing. Venetoclax or LDC may be reintroduced, but only at a reduced dose, (in consultation with the AbbVie medical monitor) if the toxicity returns to \leq Grade 1 or to baseline if Grade 2 at study entry.

Subjects should be monitored for new onset hematologic toxicity and renal toxicities, with dose delay or reduction as appropriate. Please follow local, approved product label or applicable SmPC for monitoring guidelines.

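### Table 1 returns subjects to the initial target dose when a CYP3A inhibitor is stopped, with no exception for a dose lowered for toxicity; read literally, this undoes Table 12's last step

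*Protocol*

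**What the plan says.** **Reduction for cytopenia.** Protocol Section 6.1.8.3 covers a subject still responding beyond Cycle 2 "but has persistent neutropenia or thrombocytopenia venetoclax dose may be reduced as follows". Table 12 then gives three steps, all starting from 600 mg. The first two shorten the schedule to 21 and then 14 days per 28-day cycle and keep 600 mg. The third lowers the daily dose: "400 mg daily × 14 days with 14 day interruption".

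**CYP3A inhibitors.** Section 5.2.3, Table 1, tells sites to cut venetoclax at least 2-fold with a moderate inhibitor and at least 8-fold with a strong one, and to "limit the duration to the minimal duration medically required". After the inhibitor is stopped they are to "wait for 2 to 3 days before venetoclax dose is increased back to the initial target dose".

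**What the target dose is.** Section 5.1 describes the period "until the target dose of venetoclax is achieved is considered the venetoclax ramp-up period", so the target is the dose at the end of ramp-up. For Cohort C the schema states: "Venetoclax dose will be administered at the designated cohort dose of 600 mg on Day 4". The initial Phase 2 schema also gives 600 mg. Section 5.6.4 lists target doses by dose level and expects one final target for all subjects.

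**Other toxicity rules.** After a related Grade 3 or greater nonhematologic toxicity, Section 6.1.8.5 says: "Venetoclax or LDC may be reintroduced, but only at a reduced dose". After a dose-limiting toxicity, Section 6.1.8.1 says: "The dose may be increased thereafter upon joint determination of the investigator and the AbbVie medical monitor".

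**The concern.** The two tables were written for different purposes and meet in one kind of subject: a responder already lowered to 400 mg for persistent cytopenia who then takes and stops an inhibitor. Table 12 intends 400 mg. Table 1 sends the subject to the initial target dose, which in Phase 2 is 600 mg. Table 1 has no carve-out for a dose lowered for toxicity, and no other section supplies one for a Table 12 reduction.

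The overlap is foreseeable. Section 6.1.8.3 provides for antifungal prophylaxis where indicated, just before Table 12, and points the reader to Table 1. Appendix C lists fluconazole as a moderate inhibitor and posaconazole and voriconazole as strong ones. Cohort C exists to allow strong inhibitors. Because Table 1 asks for the shortest necessary course, stopping the inhibitor is the expected sequence.

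At stake is a written instruction that can raise the daily dose in a subject whose dose was lowered for low counts. The return step does not require contact with the medical monitor, although the same table requires it when a moderate CYP3A inducer is needed at the cohort dose.

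**Working it through.** The plan gives no figure of its own here, so the check sets the tables side by side and adds dose arithmetic.

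**Inputs**
- Table 12 steps: 600 mg × 21, 600 mg × 14 and 400 mg × 14 days per 28-day cycle (Protocol Section 6.1.8.3).
- Table 2 conversions: 400 mg becomes 200 mg (moderate) or 50 mg (strong); 600 mg becomes 300 mg or 50 mg (Protocol Section 5.2.3).
- Return dose after an inhibitor: the initial target dose, 600 mg in Phase 2 (Table 1 with Section 5.1).

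**Is the on-inhibitor step at fault?** No. Table 2 has a 400 mg row and meets Table 1's minimum cuts: 400/200 = 2 and 400/50 = 8; 600/300 = 2 and 600/50 = 12. The gap is in the return step.

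**Formula:** venetoclax per cycle = daily dose × dosing days in the cycle.

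| Stage, subject at Table 12's last step | Calculation | mg per cycle |
|---|---|---|
| Before the inhibitor | 400 × 14 | 5,600 |
| On a moderate inhibitor, if converted by Table 2 | 200 × 14 | 2,800 |
| On a strong inhibitor, if converted by Table 2 | 50 × 14 | 700 |
| After stopping, Table 1 read literally | 600 × 14 | 8,400 |
| After stopping, with the fix | 400 × 14 | 5,600 |

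Ratio after stopping: 8,400 / 5,600 = 1.50, or 50% above what Table 12 intends. The 8,400 mg total equals the step before (600 × 14), so the last step is exactly reversed.

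**Earlier steps.** These stay at 600 mg daily (600 × 21 = 12,600 mg; 600 × 14 = 8,400 mg). A return to 600 mg is the right daily dose there, so nothing is undone.

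**The case against.** The strongest reply is that the literal reading is not forced. Table 1's return step is paired with its own inhibitor cut, and an increase back can be taken to reverse that cut alone. Table 2 is keyed to the assigned dose and has a 400 mg row, so 400 to 50 to 400 mg is a coherent path. Section 5.2.3 also invites sites to call the medical monitor with questions on concomitant therapy. This stands as a reason why a careful site may do the right thing. It does not clear the text: the word *initial* points to the cohort's target, not to a later individual dose, and the return step is written as an instruction.

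Reach is also limited, and that stands in full. Table 12 is optional. Only its last step is affected, and it is reached after two schedule cuts. The subject must then start and stop an inhibitor, and counts may have recovered by then. The SAP (Section 5.0, Table 1) records enrollment as complete at 92 subjects.

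Three stronger readings are tempting, and the documents do not support them:
- A reader might infer that full 28-day dosing is restored as well. Table 1 speaks of dose and never of schedule.
- A reader might infer a clash with Section 6.1.8.5 or 6.1.8.1. Those sections already limit re-escalation for the toxicities they cover, and Section 6.1.8.5 names no reduced dose from which to calculate.
- A reader might infer that Table 12's last step fails under a strong inhibitor, since Table 2 gives 50 mg for both 600 mg and 400 mg. That depends on Table 12 doses being converted by Table 2, which is not stated. Table 1 also sets a minimum cut, so 50 mg is not a floor. Whether to stop a needed anti-infective is a clinical decision, outside a wording correction.

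**Conclusion.** The point holds as a minor safety wording error. Followed as written, Table 1 raises the daily dose from 400 mg to 600 mg, 8,400 mg instead of 5,600 mg per cycle (+50%), in a Phase 2 subject lowered by Table 12's last step who then stops a moderate or strong inhibitor.

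This rests on two readings. The initial target dose is taken as the cohort's end-of-ramp-up dose, which Sections 5.1 and 5.6.4 support. The 14-of-28-day schedule is taken to continue, because Table 1 does not mention schedule. The number of subjects is unknown and likely very small. Sample size, endpoint definitions and analyses are unaffected. The rule can still matter for anyone remaining on treatment, since Section 5.1 allows venetoclax for up to 4 years after the last enrolled subject's first dose.

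**What to change.** In Table 1, replace the return dose with: *the initial target dose or, if venetoclax has been reduced for toxicity, the reduced assigned (unconverted) dose and schedule; any later increase is by agreement with the medical monitor.*

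Keeping the initial target dose as the default matters. Inhibitors are allowed during ramp-up, and Table 2 has 100 mg and 200 mg rows for it. A rule to return to the dose in use before the inhibitor would send such a subject to a ramp-up dose, or to no dose at all. The word *unconverted* makes clear that the Table 2 dose is not the one to resume. A subject whose counts have recovered can still be re-escalated by agreement.

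The cost is one phrase in an amendment, with the usual ethics committee approval. It needs no new dose level, tablet strength, procedure or data collection, and Table 12 needs no change.
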